8.4 Statistical analysis methods

8.4.1. Definition of Analysis Sets

- ITT Analysis Set (Intent-to-Treat): Includes data from all pediatric patients who received at least one session of oral rehabilitation therapy and had at least one assessment of the outcome variable.
- FAS Analysis Set (Full Analysis Set): Includes data from the ITT set, excluding patients who did not meet the eligibility criteria or failed to undergo the primary outcome assessment.
- PP Analysis Set (Per-Protocol): Includes data from the ITT set, specifically from patients who strictly adhered to the clinical trial protocol by completing direct swallowing training or both direct swallowing training and sensory-motor stimulation therapy, with outcome variables assessed.

This study will conduct ITT, FAS, and PP analyses, with FAS analysis being the primary approach.

* Subgroup Analysis: Subgroup analysis will be performed based on gestational age, birth weight, and bronchopulmonary dysplasia.

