[Protocol for Clinical Trial]

The effects of direct swallowing training and oral sensorimotor stimulation in preterm infants

2015.07

NCT02508571

Table of Contents

1. Title of the Clinical Trial	5
2. Name and Address of the Clinical Trial Institution	5
3. Study Period	5
4. Objectives of the Study	5
5. Study Design	5
6. Study Participants	5
7. Study procedures	7
8. Study evaluation	12
9. Dropout	15
10. References	16

[Clinical Trial Overview]

Clinical Trial Title	The effects of direct swallowing training and oral sensorimotor stimulation in preterm infants
Objective of the Clinical Trial	This study aims to evaluate whether the application of direct swallowing training (DST) and oral sensorimotor stimulation (OSMS) in preterm infants preparing for the transition from tube feeding to oral feeding shortens the time required for complete oral feeding and improves oral feeding skills. Additionally, the study will assess the long-term impact of oral feeding

Protocol_DST and OSMS_oral feeding performance

	interventions in the neonatal intensive care unit (NICU) on developmental outcomes and dietary habits.
Phase of the Clinical Trial	Prospective, blind, controlled, randomized trial
Clinical Trial Institution	Seoul National University Hospital
Principal Investigator	[name], Department of Pediatrics, Seoul National University College of Medicine
Study Design	single-center, prospective, open-label, controlled, randomized study
Study participants	
 -Gestational age at birth < 32+0 weeks -Eligible for respiratory support using heated humidified high-flow nasal cannula (HHFN) or equivalent, within 33+0 weeks -Infants who have been progressing with tube feeding at a volume of 120 ml/kg/day or more -Informed consent obtained from parents or legal guardians
Number of participants	189
Study methodology	
In this study, preterm infants who are receiving adequate tube feeding and have been discontinued from continuous positive airway pressure (CPAP) for at least 48 hours will be divided into three groups:
 
 - Control Group -DST Group (Direct Swallowing Training) -DST + OSMS Group (Direct Swallowing Training + Oral Sensorimotor Stimulation) 
Each group will receive its respective intervention.

Study period	From IRB approval date in 2015 to December 30, 2025.

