7.2 Randomization

In this study, eligible participants who meet all the inclusion criteria will be randomly assigned in a

Protocol_DST and OSMS_oral feeding performance

1:1:1 ratio to the control group, the DST group, or the DST + OSMS group. However, randomization will be stratified by gestational age and sex.

The randomization will be done using a block randomization method with block sizes of 3 and 6, generated through SAS 9.2. The randomization process will be managed via the MRCC website (<http://mrcc.snu.ac.kr>) using web-based randomization.

The detailed randomization procedure is as follows:

- Study coordinators will be provided with an ID and password for randomization.
- The study coordinators will log in to the MRCC website (<http://mrcc.snu.ac.kr>) and access the randomization screen.
- The study coordinator will enter the participant's basic information, test results, inclusion/exclusion criteria, and other relevant data, and click the confirmation button.
- If the participant is eligible, a randomization number will appear on the screen.
- The randomization screen will be printed, and one copy will be kept for records.
- The study coordinator will use the assigned randomization number to prescribe the corresponding intervention.

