7.3.4. Detailed method for each intervention

Both the experimental group and the control group will continue the use of non-nutritive sucking through a rubber nipple and oral support during feeding, which are currently standard practices in the neonatal intensive care unit.

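### No planned analysis set contains all randomised infants, and the primary set (FAS) selects on whether the primary outcome was obtained

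*Combined protocol and SAP*

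**What the plan says.** Section 8.4.1 defines three sets.

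- **ITT**: "all pediatric patients who received at least one session of oral rehabilitation therapy" and who "had at least one assessment of the outcome variable". Randomisation is not mentioned.
- **FAS**: the ITT set, "excluding patients who did not meet the eligibility criteria or failed to undergo the primary outcome assessment".
- **PP**: the part of the ITT set that adhered to the protocol by "completing direct swallowing training or both direct swallowing training and sensory-motor stimulation therapy", with outcomes assessed.

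All three analyses are planned, "with FAS analysis being the primary approach".

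The primary outcome (8.3.1) is a period. It runs from the start of oral feeding to full oral feeding free of feeding-related side effects that need special treatment. Section 8.4.2 lists the Mann-Whitney test and analyses of variance, and has no rule for an infant whose period is incomplete. Section 9 makes respiratory deterioration, gastrointestinal deterioration with a fast longer than 48 hours, any serious adverse event, and guardian withdrawal reasons for dropout.

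**The concern.** An intention-to-treat set keeps every randomised infant in the assigned arm, so that the arms being compared are the arms that randomisation made alike. The set given that label here requires both treatment and assessment, and the other two sets are drawn from it. The primary set then depends on whether the outcome itself was obtained.

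That matters because the outcome measures how quickly an infant learns to feed, and an infant who deteriorates may both drop out and be a slow feeder. If such infants leave the arms in different numbers or for different reasons, the remaining infants no longer form a randomised comparison. A difference in days could then be created, hidden or exaggerated.

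Two wording matters add to this. The term *oral rehabilitation therapy* occurs only in 8.4.1 and is not defined, and the PP rule describes completion only for the two active arms. Whoever runs the analysis would have to supply the control-arm wording.

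**Working it through.** **1. Who can be lost at each step.**

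| Step | Condition in 8.4.1 | Infant lost |
|---|---|---|
| Randomised to ITT | at least one session | randomised, never had a session |
| Randomised to ITT | at least one outcome assessment | left before any assessment |
| ITT to FAS | eligible | found ineligible later |
| ITT to FAS | primary outcome assessed | no start of oral feeding, or no qualifying full oral feeding, on record |
| ITT to PP | adherence by completion | incomplete course |

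FAS and PP are subsets of ITT, and ITT omits the first two kinds of infant. So no set is defined as all randomised.

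**2. How much each step may matter.**

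- *No session.* Randomisation (7.2) and the start of intervention (7.3.1) are described under separate conditions. But the Overview has infants divided into groups when already on adequate tube feeding and off CPAP for 48 hours, which matches the feeding and CPAP conditions of 7.3.1. Losses here may be few or none.
- *Ineligible.* In 7.2 the web system issues a number only after eligibility is confirmed, so this should also be small.
- *No primary outcome.* This is the step that bears on the result, because three of the section 9 reasons are clinical events that may go with slow feeding progress.

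**3. Does running ITT beside FAS solve it?** Only in part. If the outcome variable in the ITT definition means any outcome, ITT can keep a dropout who had, say, the first feeding evaluation of 8.2.3. That infant still has no value in days. For the primary outcome, the ITT analysis then either reduces to the infants with a value, which is FAS apart from ineligible infants, or needs a rule that 8.4.2 does not give.

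**4. The plan's own figures.**

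Inputs from 6.2: smallest difference 14.6 − 10.0 = 4.6 days, SD 7.19, two-sided alpha 0.0167, power 80%, dropout 10%.

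- Normal approximation: n = 2 × (2.393 + 0.842)² × 7.19² / 4.6² = 51.1, so 52 per group. The t-test gives 53.
- 53 × π/3 = 55.5, so 56, which matches the plan. That the plan used a Mann-Whitney adjustment is my inference, since 6.2 does not name the test.
- 56 / 0.9 = 62.2, rounded up to 63 per arm, and 63 × 3 = 189, which matches.
- Allowance for loss: 189 − 168 = 21, and 21/189 = 11.1% (the stated 10% after rounding up within arms). That is 63 − 56 = 7 per arm.

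Power for the 4.6-day contrast by normal approximation is 88.4% with 63 per arm, 83.9% with 56 and 79.0% with 50. Within the planned allowance, power is not the problem.

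**5. Controls.** Read literally, the undefined therapy term does not cover them: 7.3.2 schedules sessions only for the DST and DST + OSMS groups, and the blinding section (numbered 10.4.3.3, within section 7) has no procedure done during the control visit. Against that:

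- The Overview says "Each group will receive its respective intervention".
- In 7.2, "The study coordinator will use the assigned randomization number to prescribe the corresponding intervention" applies to every randomised infant.
- In 7.3.4, "Both the experimental group and the control group will continue the use of non-nutritive sucking", along with oral support.
- The blinding section gives controls a 15-minute screened visit at the same times as the active arms.
- Hypotheses 1 and 2 in 6.2 compare against controls.

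The intention to analyse controls is clear. The wording of the ITT and PP definitions does not carry it out.

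**The case against.** The strongest reply is that little may be lost. If nearly all infants are treated soon after randomisation and are followed to full oral feeding, the ITT set as defined would be close to all randomised. Nothing in section 9 says that an infant who meets a dropout criterion loses the primary outcome. Section 8.1 lists full oral feeding and discharge among the recorded points, and the documents do not say whether recording stops at dropout. All of this stands. It limits what can be said about size, but it does not supply a set of all randomised infants or a rule for those without a value.

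Three stronger readings are tempting, and the documents do not support them.

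- *Controls would be excluded from the trial's analyses.* This follows only from the literal wording of one undefined term. The text listed in step 5 of the working shows otherwise.
- *Only Hypothesis 3 can be tested in PP.* This too rests on the literal completion clause. The governing condition in PP is adherence to the protocol, and the missing control clause is a drafting omission of the same kind. PP is also not the primary set.
- *21 infants, or 7 per arm, will leave FAS.* That is the dropout allowance. How many of those infants would lack the primary outcome is not stated, and an even split between arms says nothing about imbalance.

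**Conclusion.** The point holds: as written, no planned analysis includes all randomised infants, and the primary one excludes infants according to whether the primary outcome was obtained, with no rule for incomplete periods. This can bias the comparison of days to full oral feeding if dropout is related to feeding progress. The section 9 reasons make that plausible, but the documents do not establish it. Neither the size nor the direction of any bias can be derived. The control-entry and PP points are secondary wording defects.

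I rate this as should-fix. The conclusion about the sets rests on the text of 8.4.1 alone. The conclusion about bias rests on two assumptions: that some section 9 dropouts have no primary outcome recorded, and that they differ in feeding progress from infants who stay.

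**What to change.** 1. Define ITT as all randomised infants in their assigned arm and make it the primary set. Report by arm how many never started oral feeding and how many did not reach full oral feeding.
2. State how infants without a value in days enter that analysis. One option is a rank-based comparison (Mann-Whitney is already listed in 8.4.2) in which infants who have not reached full oral feeding by discharge or last observation take the worst rank. Another is a time-to-event comparison with those infants censored at last observation. The second assumes that censoring is unrelated to feeding progress, and it needs a further rule for infants who never start oral feeding, because their clock has no origin.
3. Keep the complete-case comparison of days (the current FAS) as a supporting analysis. After a section 9 event, continue to record feeding milestones where consent allows, and record the date of dropout, which 8.1 does not list.
4. If a modified set is kept, replace *oral rehabilitation therapy* with one condition for all three arms, such as at least one real or sham session, and say which outcome must have been assessed. Add a control clause to PP: sham visits completed and no DST or OSMS received.

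The cost is a rewording of 8.4.1, a modest amount of extra analysis and one extra recorded date. The new primary analysis carries an assumption about infants without a value, which the supporting analysis checks.

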8.4.2 Statistical Analysis Methods

- Statistical Software: SPSS for Windows (version 19.0)
- Continuous Variables: Mann-Whitney U test, One-way ANOVA
- Categorical Variables: Chi-square test, Fisher's exact test
- Evaluation of the Effect of Interventions on Primary and Secondary Outcomes:
 - Two-way analysis of variance
 - Repeated measures analysis of variance
 - Post-hoc analysis, if necessary
- Univariate/Multivariate Analysis: Binary and multiple logistic regression analysis
- Unless otherwise specified, all statistical tests will be conducted at a two-sided significance level of 0.05.

9. Drop out

<Criteria for Clinical Trial Dropout>

- When the guardian requests discontinuation of the clinical trial or withdraws consent for participation.
- When the participant experiences respiratory deterioration during the trial period, requiring the use of a respiratory device beyond nasal positive pressure ventilation.
- When the participant experiences gastrointestinal deterioration during the trial period, necessitating fasting for more than 48 hours.
- When a serious adverse event occurs.

10. References

- 1) American Academy of Pediatrics Committee on Fetus and Newborn. Hospital discharge of the high-risk neonate. *Pediatrics* 2008;122:1119-26.
- 2) Bragdon DB. A basis for the nursing management of feeding the premature infant. *JOGN Nurs* 1983;12(3 Suppl):51s-7s.
- 3) Gryboski JD. Suck and swallow in the premature infant. *Pediatrics* 1969;43:96-102.
- 6) Bingham PM. Deprivation and dysphagia in premature infants. *J Child Neurol* 2009;24:743-9.

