6.2 Target sample size and rationale for calculation

The primary objective of this study is to determine whether there is a difference in the time taken to reach full oral feeding, from the initiation of oral feeding, when DST and OSMS are applied to preterm infants preparing for the transition from gavage feeding to oral feeding.

To calculate the sample size required to achieve the research objective, the following assumptions are made:

Protocol_DST and OSMS_oral feeding performance

(1) Level of significance (α): 0.0167 (two-tailed test).

When comparing the control group with the DST group, the control group with the DST + OSMS group, and the DST group with the DST + OSMS group, there is an issue of multiple comparisons. To address this, Bonferroni correction is applied. The significance level used is $0.05/3 = 0.0167$.

(2) Group ratio: Control group : DST group : DST + OSMS group = 1 : 1 : 1.

(3) Type II error (β): 0.20, maintaining a test power of 80%.

(4) Primary outcome: Days from start to full oral feeding (SOF-FOF).

(5) The hypothesis of the study is as follows:

[Hypothesis 1]

Null hypothesis: There is no difference in SOF-FOF days between the control group and the DST group.

Alternative hypothesis: There is a difference in SOF-FOF days between the control group and the DST group.

[Hypothesis 2]

Null hypothesis: There is no difference in SOF-FOF days between the control group and the DST + OSMS group.

Alternative hypothesis: There is a difference in SOF-FOF days between the control group and the DST + OSMS group.

[Hypothesis 3]

Null hypothesis: There is no difference in SOF-FOF days between the DST group and the DST + OSMS group.

Alternative hypothesis: There is a difference in SOF-FOF days between the DST group and the DST + OSMS group.

(6) Sample size calculation method: The PASS program (Power Analysis and Sample Size software; <http://www.ncss.com>) will be used.

Based on existing research data (16, 18), the average SOF-FOF days for each group were assumed as follows: Control group 20.8 days, DST group 14.6 days, and DST + OSMS group 10.0 days. The pooled standard deviation was calculated to be 7.19. With a significance level of 1.67% and a two-tailed test, the required sample size for 80% power is 56 participants per group, for a total of 168 participants.

Protocol_DST and OSMS_oral feeding performance

Assuming a 10% dropout rate, the final sample size, accounting for dropouts, is 189 participants.

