8.3 Outcome

8.3.1. Primary outcome: The period from the start of oral feeding to the time when full oral feeding is achieved without any feeding-related side effects requiring special treatment.

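### The primary outcome is a time to an event, but the plan compares completers only: the planned error rate and power hold under equal 10% loss, not if loss differs by arm and falls on slow feeders

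*Combined protocol and SAP*

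**What the plan says.** - **Outcome (8.3.1).** "The period from the start of oral feeding to the time when full oral feeding is achieved without any feeding-related side effects requiring special treatment". The first two secondary outcomes in 8.3.2 are also periods that run from the first oral feed to a feeding milestone.
- **Methods (8.4.2).** "Continuous Variables: Mann-Whitney U test, One-way ANOVA". For the effect of the interventions on primary and secondary outcomes the section lists "Two-way analysis of variance", repeated-measures ANOVA and post-hoc analysis. Chi-square, Fisher's exact test and logistic regression are listed as well. It gives no rule for censoring, imputation or ranking of infants without the event.
- **Analysis set (8.4.1).** The FAS is primary. It drops ineligible infants and those without the primary outcome assessment.
- **Leaving the trial (section 9).** The reasons are withdrawal by the guardian, respiratory deterioration, gastrointestinal deterioration with prolonged fasting, and a serious adverse event.
- **Allowance for loss (6.2).** "Assuming a 10% dropout rate", the total becomes 189. No loss is given by arm or by feeding speed.

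**The concern.** For an infant who leaves on day x before full oral feeding, the data say that the time exceeds x. As 8.4.2 stands, that information has no place in the analysis, and the FAS rule removes the infant. The ITT set does not help: an infant kept there without a date still gives ANOVA no value.

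The infants lost need not be typical. A slow infant is exposed to the risk of leaving for longer, so completers are faster than average even when leaving has nothing to do with the infant's condition. Two of the four reasons in section 9, respiratory and gastrointestinal deterioration, may also be linked to slow feeding. The arm that loses more such infants looks faster than it is. Depending on which arm that is, a real effect shrinks or a false one appears. Inflating the sample to 189 replaces numbers but does not remove this bias.

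**Working it through.** **1. The plan's own figure.** Inputs from 6.2: "Control group 20.8 days, DST group 14.6 days, and DST + OSMS group 10.0 days"; SD 7.19; two-sided α = 0.05/3 = 0.0167; power 80%. The smallest contrast is 14.6 − 10.0 = 4.6 days.

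- Normal approximation: n = 2(z₁₋α/₂ + z₁₋β)²σ²/δ² = 2 × (2.394 + 0.842)² × 7.19²/4.6² ≈ 51.2, so 52 per group.
- t-test: 52.6, so 53.
- Mann-Whitney: 52.6 × π/3 = 55.1, so **56**, as stated.
- Dropout: 56/0.90 = 62.2, so 63 per group; 63 × 3 = **189**, as stated.

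With 56 evaluable per group, power for 4.6 days is 80.8% (Mann-Whitney) or 82.8% (t-test). Purely random loss at 10% therefore keeps 80%.

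**2. Leaving at a constant daily rate λ, unrelated to condition (assumption).** If times are gamma with mean μ and SD σ, completers have mean μ²/(μ + λσ²). Here σ² = 51.70.

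- Equal rates, λ = 0.0086 in both arms (about 12% v 8% lost): 213.16/15.045 − 100/10.445 = 14.17 − 9.57 = 4.59 days. The contrast is intact, because each mean moves by roughly λσ² and the shifts cancel.
- Unequal rates, 0.0146 v 0.005 (about 19% v 5% lost): 213.16/15.355 − 100/10.258 = 13.88 − 9.75 = 4.13 days. Simulation gave 4.12 days, with power of 75% (t-test) and 89% (Mann-Whitney).
- No true difference (both 14.6), leaving in one arm only at 10% / 19% / 34%: t-test error 2.1% / 3.3% / 7.9%, Mann-Whitney 1.6% / 3.0% / 7.5%.

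**3. Leaving weighted to slow feeders (assumption).** Simulated trials had 63 per arm, gamma times, SD 7.19 and α = 0.0167. The chance of leaving was proportional to the squared rank of the infant's time. Unless noted, leavers were censored at 50–100% of their true time. The t-test stands in for the pairwise ANOVA contrast. Ranges cover independent runs.

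| Scenario | t-test, completers | Mann-Whitney, completers | Generalised Wilcoxon, all infants |
|---|---|---|---|
| No effect, 10% v 10%: error | 1.8–1.9% | – | – |
| No effect, 20% v 5%: error | 6.3–7% | 5.7–7% | 1.2–1.5% |
| Same, but leaving early (first 30% of own time, or near the start): error | 6.0–6.7% | – | 5.4–6.4% |
| 14.6 v 10.0, 10% v 10%: power | 86–87% | – | – |
| 14.6 v 10.0, 15% v 5%: power | 72–74% | 86–88% | 95% |

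In the last row the completer difference is about 3.9 days, a loss of 4.6 − 3.9 = 0.7 days. Across normal, gamma and lognormal times, t-test power there was 68–74%. A mild imbalance of 12% v 8% gave t-test error of 2.1% and power of 81%.

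**4. Choice of test.** The generalised Wilcoxon statistic scores each pair of infants by which is known to be faster. With no censoring that is the Mann-Whitney statistic, so the test behind 56 per group is kept. A log-rank test had power of only 72–75% at 63 per arm under these gamma times, so adopting it would mean redoing the sample size.

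**The case against.** A reader might infer that slow feeders vanish from the trial, that the listed methods cannot use infants without the event, or that the planned error rate and power are lost outright. The documents support none of these.

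- Slowness is not a reason for leaving in section 9; a slow infant who reaches full oral feeding is counted.
- Mann-Whitney could rank non-achievers last. The plan merely has no rule that says so.
- The harm is conditional. The documents give no loss by arm, and equal 10% loss leaves both figures in place. The 20% v 5% case averages (20 + 5)/2 = 12.5% over the two arms, above the planned 10%; the 15% v 5% case averages 10%.
- The power loss is largely a t-test problem. Completer Mann-Whitney stays above 80% at 15% v 5%; its weakness is false positives. The other two contrasts keep about 96% and 100% t-test power there.

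Two further objections shape the remedy. Section 9 does not say that data recording stops when an infant leaves, and 8.1 already lists the feeding milestones and length of stay. Dates may therefore exist, and censoring at withdrawal would then discard real data. Also, censoring is no cure when slow feeders leave early, as the third row of the table shows.

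All of this stands. It limits the size of the point. It does not supply the missing rule: as written, infants without the assessment are removed and no listed method uses their partial time.

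**Conclusion.** The point holds in a conditional form. The plan leads to a completers-only comparison of a time-to-event outcome. If loss is equal across arms at the planned 10%, the 1.67% error rate and 80% power hold. The one exception seen was an extreme: if the leavers are exactly the slowest 10% in both arms, t-test error is 4.3%, with no loss of power.

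If loss differs by arm and falls on slow feeders, error is about 6–7% for both the t-test and Mann-Whitney (assumed 20% v 5%, no effect). Under the planned effect (assumed 15% v 5%), the 4.6-day contrast falls to about 3.9 days and t-test power to about 70–74%, with Mann-Whitney near 86–88%. These sizes rest on the assumed loss patterns and mainly on gamma times; none is forecast by the documents. The plan should be changed because the safeguard is cheap, not because harm is shown to be likely.

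**What to change.** 1. **8.4.1 and section 9.** State that the feeding dates listed in 8.1 continue to be recorded after an infant stops the intervention, unless consent is withdrawn, and that these infants stay in the primary analysis.
2. **8.4.2.** For the primary outcome and the two other feeding-period outcomes, name Kaplan-Meier curves and three pairwise generalised Wilcoxon (Gehan-Breslow) tests. State 0.0167 there, since the section otherwise defaults to 0.05. Censor only infants whose feeding date is truly unobserved, at the last feeding record. Report the difference in median days, or in restricted mean days to a horizon fixed before analysis, with a confidence interval.
3. **Sensitivity.** Rank infants who left for clinical deterioration behind all who reached full oral feeding.
4. **Reporting.** Give by arm the number who left before the first oral feed. The intervention starts during tube feeding (7.3.1), so these infants have no time origin and cannot simply be censored.

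The cost is plan wording, continued recording of items already listed, and slightly more analysis; no extra infants are needed. The small downside is that the effect is no longer a raw mean difference, and the rank test and the reported estimate are different quantities. Another censoring-aware test would be acceptable if the sample size were re-derived for it.

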8.2.3. Indicators for evaluating oral feeding performance

Data will be collected through three evaluations:

- 1) The time point when oral feeding starts,
- 2) The time point when oral feeding volume reaches 50% of total feeding volume,
- 3) The time point when oral feeding volume reaches 100% of total feeding volume.

-Overall transfer (% volume taken/volume prescribed)

-Proficiency (% volume taken at 5 min/volume prescribed)

Protocol_DST and OSMS_oral feeding performance

- Rate of transfer (mL/min volume of milk consumed relative to the duration of the oral Feeding session)
- Volume loss (% volume of milk spilled from the lips as a percentage of the total milk transferred)

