8.2.4. Neonatal Oral Motor Assessment Scale (NOMAS)

Evaluation time points:

- 1) Between 3-5 days after the start of oral feeding,
- 2) Within 3 days after the end of the intervention.

8.2.5. Korean Developmental Screening Test for Infants and Toddlers (K-DST), Strengths and Difficulties Questionnaire (SDQ), Behavioral Pediatric Feeding Assessment Scale (BPFAS)

Survey time point: 48 months of age \pm 3 months

Survey method: The survey will be conducted by implementing a web-based questionnaire, which will be sent via email or smartphone and returned through the same method.

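### Repeated-measures ANOVA with no missing-data rule would drop any infant who misses one feeding-performance or NOMAS assessment; a mixed model would keep the scores already observed

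*Combined protocol and SAP*

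**What the plan says.** All references are to the combined protocol and SAP.

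- **Method (Section 8.4.2).** Two-way ANOVA, "Repeated measures analysis of variance" and post-hoc analysis stand together as the ways to evaluate the interventions on primary and secondary outcomes. No method is tied to a named endpoint. A separate line reads "Continuous Variables: Mann-Whitney U test, One-way ANOVA". The software is SPSS 19.0. There is no missing-data rule, imputation or mixed model.
- **Feeding performance (Section 8.2.3).** "Data will be collected through three evaluations": at the start of oral feeding, at half of total volume, and finally "The time point when oral feeding volume reaches 100% of total feeding volume".
- **NOMAS (Section 8.2.4).** It is scored twice: "Between 3-5 days after the start of oral feeding" and "Within 3 days after the end of the intervention". Section 7.3.3 ends the intervention only after two days in a row of problem-free oral feeding at every feed.
- **Analysis sets (Section 8.4.1).** ITT requires one outcome assessment. FAS, the primary set, also removes ineligible infants and those without a primary outcome assessment.
- **Dropout (Section 9).** Reasons are withdrawal by the guardian, respiratory deterioration, gastrointestinal deterioration "necessitating fasting for more than 48 hours", and serious adverse events.

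**The concern.** Classical repeated-measures ANOVA needs a full set of scores from each infant. This is a property of the method; the protocol does not mention it. With no other rule in the plan, an infant with two of the three feeding evaluations, or one of the two NOMAS scores, would contribute nothing.

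Two things are at stake. The first is precision, because valid scores are thrown away. The second is selection. The last assessment of each kind is reached only through feeding progress, and two of the dropout reasons are clinical deterioration. The infants left in the analysis may therefore be better feeders than those randomised, and not to the same degree in each arm if the interventions work.

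**Working it through.** **1. The plan's own figure.** Section 6.2 sizes the trial for the primary outcome. The smallest pairwise difference is 14.6 − 10.0 = 4.6 days, with SD 7.19, two-sided alpha 0.0167 and power 80%. The normal formula gives 52 per group and the noncentral t gives 53. The t-test number with the Mann-Whitney efficiency correction is 53 × π/3 = 55.5, so 56, which matches the plan. For dropout, 56/0.90 = 62.2, so 63 per group, and 3 × 63 = 189. Both stated figures reproduce. Neither says anything about missing feeding-performance or NOMAS scores.

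**2. Which endpoints the method can serve.** The other outcomes in Section 8.3 are single durations or tests scheduled at one age. Feeding performance and NOMAS are the only ones scheduled repeatedly, so they are the natural targets. This is an inference from the schedule.

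**3. Who would be deleted.**
- In the ITT set: infants with at least one assessment but not all of them. The set admits them and the method removes them.
- In the FAS: infants who reach full oral feeding, and so have the primary outcome, but miss the 50% evaluation or a NOMAS window.

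**4. Ceiling from the plan's dropout rate.** If all of the 10% fell on the last assessment, 0.10 × 189 = 18.9 infants would lose earlier scores and 170.1 would remain. This is a maximum. The intervention starts during gavage feeding (Section 7.3.1) and the first feeding evaluation comes at the start of oral feeding, so infants who drop out in between have no feeding score to lose.

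**5. Illustration of precision loss.** Assume a proportion p is missing independently at each of three assessments. Complete cases are then (1 − p)³, and the standard error relative to full data is 1/√(complete fraction).

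| p (assumed) | Complete | Excluded | Per arm of 63 | Standard error vs full data |
|---|---|---|---|---|
| 5% | 0.857 | 14% | 54.0 | 1.08 |
| 10% | 0.729 | 27% | 45.9 | 1.17 |
| 15% | 0.614 | 39% | 38.7 | 1.28 |

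For two NOMAS scores at p = 10%, 189 × 0.90² = 153.1 infants remain. A mixed model recovers part of this loss, not all of it. Purely independent missingness costs precision but does not produce selection.

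**6. Illustration of selection.** A simulation used two arms of 63, three normal scores with correlation 0.6, a constant arm effect, and loss of the third score driven by poor first-assessment performance under the same rule in both arms (2,000 replicates). The effect is averaged over the three assessments.

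| True effect (SD) | Control loss | Complete cases | All observed scores |
|---|---|---|---|
| 0.30 | 10% | 0.28 | 0.31 |
| 0.30 | 20% | 0.26 | 0.30 |
| 0.50 | 10% | 0.46 | 0.50 |
| 0.50 | 20% | 0.43 | 0.50 |

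Complete cases shrink the effect by about 8–9% at 10% loss and 13–14% at 20%. With no true effect the bias was about zero. These results depend on the assumed correlation and loss rule, neither of which the plan supplies.

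**The case against.** Much of the case on the other side stands.

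- **The plan does not assign the method.** A reader might infer that the feeding and NOMAS scores will definitely be analysed this way. Section 8.4.2 does not say so. The Mann-Whitney test and one-way ANOVA could be run at each assessment on whoever is available. However, the plan never says that they replace the repeated-measures analysis, which has no other scheduled use.
- **FAS already does part of the removal.** Infants who never reach full oral feeding probably lack the primary outcome assessment and leave the primary set under any model. Within FAS, deletion falls mainly on assessments missed for other reasons. Replacing the ANOVA without widening the set would therefore not bring the first group back.
- **Loss is not only poor feeding.** Withdrawal of consent or a missed window also causes it. A reader might infer that the comparisons will rest on infants who fed well. The documents support only that this may happen. Nor are the 14–39% exclusions evidence of it, since they assume independent missingness.
- **The mixed model has limits.** A score at the 100% milestone is undefined, not merely unobserved, for an infant who never gets there. Overall transfer at that milestone is likely to be near its ceiling. The documents do not say how NOMAS is scored, so a linear model for it is not yet justified.

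These points limit the size and the wording of the concern. They do not supply a missing-data rule or a reason to discard observed scores.

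**Conclusion.** The point holds for secondary outcomes only. If the listed repeated-measures ANOVA is applied in its classical form to the outcomes it fits, infants with partial data are dropped, which is at odds with an ITT set that admits them on one assessment. The certain consequence is lost precision. Over-representation of better feeders is plausible, because the last assessments depend on milestones, but it is not demonstrated.

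The size cannot be fixed from the documents. At most about 19 of 189 infants would lose earlier data if the 10% dropout all fell on the last assessment. Under the simulation's assumptions, that level of loss weakens a real effect modestly and creates no false one when the loss rule is the same in each arm. A reader might infer a threat to the main result. There is none, because the primary outcome is one duration per infant. The change is still worth making: it improves a stated method at almost no cost.

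**What to change.** - **Method.** In Section 8.4.2, name the analysis for each endpoint. For the feeding-performance measures, replace repeated-measures ANOVA with a linear mixed model: arm, assessment, arm-by-assessment, gestational-age stratum and sex (the randomisation stratifiers in Section 7.2), with unstructured covariance. Give arm contrasts at each assessment. Do the same for NOMAS only if its score is suitable for a linear model.
- **Analysis set.** Use every randomised infant with at least one assessment of the endpoint, not only the FAS.
- **Reporting.** Tabulate missing assessments by arm with reasons, and state how missing data are handled.
- **Interpretation.** State that the contrast at the 100% milestone either applies to infants who reach it or rests on a missing-at-random assumption.

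**Cost.** SAP wording and slightly more modelling work. The SPSS MIXED procedure can fit the model, and no new data are needed. The price is reliance on missing-at-random and approximate normality, the latter most doubtful for measures near a ceiling.
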